7.1.2 Secondary Outcomes

Progression-free survival time, Overall survival time, Cytomegalovirus occurrence and severity , Epstein-Barr virus occurrence and severity, BK virus occurrence and severity

All time-to-event outcomes will be measured from the time of CYT107 administration, with a maximum follow up of at least 12 months.

7.2 Baseline covariates

Baseline patient covariates to be recorded at enrollment will include the following variables:

Conditioning regimen received
GVHD prophylaxis
Type of donor
Type of graft
Time to engraftment from cell infusion
Donor age
Acute (grades 2 – 4) GVHD
Patient age
Time to neutrophil engraftment
Time to platelet engraftment
Disease (AML or MDS)

7.3 Trial Conduct

7.3.1 Dose Assignments

Three dose levels of CYT107 will be considered: 5, 10, and 15 mcg/kg, hereafter denoted as dose levels 1, 2, and 3.

Randomization, rather than conventional sequentially adaptive dose selection, is based on the fact that neither $\text{Pr}(\text{DLT})$ nor any biological outcomes are necessarily monotone increasing in

dose of the biological agent IL-7, and also the scientific goal to obtain unbiased comparisons between doses.

A maximum of 21 patients will be randomized among the three IL-7 doses, with the randomization constrained to have exactly 7 patients per dose. Since 2 patients previously have been enrolled and assigned to d=1, a randomization sequence will be provided for assigning doses to the remaining 19 patients, 3 – 21.

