4.0 Treatment Plan and Study Design

CYT107 will not be administered before Day 60 but could be started as late as Day 180 post-CBT or haplo-SCT.

The active treatment period will be from the first injection of CYT107 and for 30 days after the last injection. The follow-up period will be for three years after the last injection.

Patients will be treated with CYT107 by intramuscular route (I.M.)* post CBT or haplo-SCT (from 60 to 180 days), with 1 of 3 doses below:

- 5 mcg/kg/dose for 3 doses, one week apart
- 10 mcg/kg/dose for 3 doses, one week apart
- 20 mcg/kg/dose for 3 doses, one week apart

Enrollment of the first 3 participants will be staggered by 14 days. Accrual in between cohorts will be halted for 30 days after the last patient in each cohort has received the last dose of CYT107.

* If the patient's platelet count is below 35,000, the product may be administered by subcutaneous route.

All patients will receive foscarnet for the management of CMV infection as per Stem Cell Transplantation and Cellular Therapy Department's standard of care.

Dose modifications

Treatment will be permanently discontinued for patients developing grade 3 or 4 GVHD, secondary graft failure, disease relapse, PTLD, PML, grade 2-4 skin rash, or grade 3-4 non-hematological toxicity attributable to CYT107.

Patients who develop grade 2 non-hematological toxicity attributable to the CYT107 will have the next dose withheld until the toxicity resolves to grade 1. If the toxicity resolves within 2 weeks the drug will be administered at the same dose, however if the toxicity takes more than 2 weeks to resolve the drug will be administered at the next lower level, or permanently discontinued if the patient was already at the lowest level. If the toxicity takes more than 4 weeks to improve to grade 1, the CYT107 will be permanently discontinued

For patients who at study entry have grade 0, 1 or 2 hematological toxicity and develop grade IV hematological toxicity attributable to the CYT107 will have the next dose withheld until the toxicity resolves to grade 2. If the toxicity resolves within 2 weeks the drug will be administered at the same dose, however if the toxicity takes more than 2 weeks to resolve the drug will be administered at the next lower level, or permanently discontinued if the patient was already at the lowest level. If the toxicity takes more than 4 weeks to improve to grade 2, the CYT107 will be permanently discontinued

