A flip-top vial is restricted for use by a single patient. Take no more than 0.5 mL into the syringe. The dose to be injected will be divided as necessary into intramuscular injections so that each injection will not exceed 0.5 mL in volume. (Dosing guidelines for ideal body weight make the requirement for multiple injections highly unlikely).

Body Weight (BW) Calculation

If patient is \leq 20% of ideal body weight (IBW), use actual weight.

In obese patients, a corrected weight will be used to calculate the final dose the patient will receive. The corrected dose will be calculated and used if the patient's actual weight give a Body Mass Index (BMI) at the upper limit of normal (i.e. BMI >30).

BMI=weight (Kg)/[height(m)]²

A BMI calculator is provided by www.cdc.gov:

https://www.cdc.gov/healthyweight/assessing/bmi/adult_bmi/english_bmi_calculator/bmi_calculator.html

If BMI >30 proceed with the following steps to determine the adjusted body weight for the dose calculation:

- Determines Ideal weight (1 kg=2.2 lbs):
 - Males: 50 kg + (2.3kg/inch over 5 ft)
 - Females 45.5 kg + (2.3kg/inch over 5 ft)
- Determine Adjusted Body weight:
 - Ideal Weight + 0.25 (actual weight - ideal weight)= Adjusted Body Weight

CYT107 Presentation and Packaging

CYT107 is supplied as a sterile colorless liquid in 2 cc glass vials that are packed individually in cardboard box. Labels are stuck on vial and box.

The labeling is following local and GMP rules. The detailed description of labeling is provided in the Pharmacy Manual.

CYT107 Storage Accountability and Return of Unused Product

Study product will be stored frozen at -25°C to -10°C until used.

The Investigational Pharmacy will maintain complete records of all study products received, stored and subsequently dispensed.

Per MDACC standard, empty, partially used, and expired vials will not be retained. These vials will be discarded immediately upon use in accordance with waste stream policy.

MD Anderson's Investigational Pharmacy Services will use its electronic accountability system in lieu of sponsor-provided accountability forms.

The detailed procedures to be followed are provided in the Pharmacy Manual.

Study Drug Administration

Each dose of CYT107 will be administered by a registered nurse. CYT107 will be administered by intramuscular route at the dose of 5, 10 or 20 mcg/kg based on the patient's body weight and the dose escalation cohort. (See Body Weight (BW) Calculation above.)

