The detailed procedures to be followed are provided in the Pharmacy Manual including a table of volumes to be administered per patient total body weight.

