7.6 Trial Conduct

The Biostatistics Department Clinical Trial Conduct Website will be used to assign a dose to each patient at enrollment. This will be set up and overseen by a Research Statistician in the Biostat Dept to be designated by [name] prior to re-starting the trial at patient number 3, using a randomization sequence provided by [name]. The Principal Investigator and designated personnel in the SCT Dept will be responsible for recording all baseline covariates and outcome variables and implementing the within-dose stopping rule in terms of DLTs.

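### The top CYT107 dose is 20 mcg/kg in Sections 4.0 and 5.1 but 15 mcg/kg in Section 7.3.1, and nothing says which prevails

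*Combined protocol and SAP*

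**What the plan says.** Three sections of the current text state the dose levels.

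- **Section 4.0 (Treatment Plan and Study Design)** offers each patient one of three doses. The lower two are 5 and 10 mcg/kg; the highest is "20 mcg/kg/dose for 3 doses, one week apart". For a toxicity that is slow to resolve, the same section says "the drug will be administered at the next lower level".
- **Section 5.1 (Study Drug Administration)** says CYT107 is "administered by intramuscular route at the dose of 5, 10 or 20 mcg/kg". It refers to a Pharmacy Manual "including a table of volumes to be administered per patient total body weight"; that table is not reproduced.
- **Section 7.3.1 (Dose Assignments)** says: "Three dose levels of CYT107 will be considered: 5, 10, and 15 mcg/kg, hereafter denoted as dose levels 1, 2, and 3". It fixes 7 patients per dose and a maximum of 21. It adds: "Since 2 patients previously have been enrolled and assigned to d=1".

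Section 7.6 says a trial conduct website "will be used to assign a dose to each patient at enrollment", to be set up "prior to re-starting the trial at patient number 3". It does not repeat the doses in mcg/kg.

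**The concern.** Dose is the experimental variable here. Section 1.0 makes safety and the optimal biologic dose the primary objective and uses the biological data to choose the phase II dose. Section 7.5.3 names one dose as optimal. If level 3 is chosen, the protocol does not say whether that means 15 or 20 mcg/kg, and any toxicity rate reported for level 3 carries the same doubt.

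There is also a treatment question. Doses are randomised rather than escalated in sequence, so a patient could be assigned to level 3 soon after the restart. Section 2.2 reports that, in mice, longer and higher-dose IL-7 lowered the number of T cells needed to cause lethal GVHD. The size of the top dose is therefore not a neutral detail.

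**Working it through.** **The statements side by side**

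| Section | Lowest | Middle | Highest |
|---|---|---|---|
| 4.0 Treatment Plan | 5 | 10 | 20 mcg/kg |
| 5.1 Study Drug Administration | 5 | 10 | 20 mcg/kg |
| 7.3.1 Dose Assignments | 5 | 10 | 15 mcg/kg |

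All three are operative text, not a record of changes, and none of the figures is blacked out. Each section lists three doses, so a fourth arm does not reconcile them.

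**Size of the difference**

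- Per injection: 20/15 = 1.33, so 20 is 33% above 15.
- Per course of three injections: 3 × 20 = 60 mcg/kg and 3 × 15 = 45 mcg/kg, a difference of 15 mcg/kg.
- Step up from level 2: 20/10 = 2.0-fold, or 15/10 = 1.5-fold.
- Reduction from level 3 to level 2 under the Section 4.0 rule: 1 − 10/20 = 50%, or 1 − 10/15 = 33%.

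**Patients concerned**

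The plan is 7 + 7 + 7 = 21. Two are already at level 1, so 21 − 2 = 19 remain: 5 at level 1, 7 at level 2 and 7 at level 3. Reallocation under Section 7.4 could move the level-3 number either way.

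**Does the product-handling text settle it?**

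Section 5.1 gives a concentration of 2 mg/mL and a limit of 0.5 mL per injection, which is 1,000 mcg. One injection is then enough up to 1000/20 = 50 kg at the higher dose, or 1000/15 = 66.7 kg at the lower. For an assumed dosing weight of 70 kg:

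- 20 mcg/kg: 70 × 20 / 2000 = 0.70 mL
- 15 mcg/kg: 70 × 15 / 2000 = 0.525 mL

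Both exceed 0.5 mL, so the volume limit does not identify the intended dose.

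**Does the dose enter the statistical design?**

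The Section 7.3.2 rule stops accrual to a dose when the posterior probability that its DLT rate exceeds .35 is above .85, under a beta(.35, .65) prior. Its only data inputs are the number of DLTs and the number of patients evaluated at that level. The mcg/kg value appears nowhere in it, so correcting the dose changes neither the stopping boundaries nor the sample size.

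**The case against.** The strongest reply is that both sections that direct treatment say 20 mcg/kg and only the statistical section differs. That section then works with levels 1, 2 and 3, so a single wrong number in Section 7.3.1 is a reasonable reading. One website assigns doses and one pharmacy table sets volumes, so all level-3 patients may well receive the same dose. The data would then attach to the dose actually given, and the harm would be one misstated number. The percentages above only restate 20 against 15: the documents give no dose-toxicity figure that converts the gap into risk, and Section 7.3.1 itself says toxicity need not rise with dose.

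Much of this is fair. Uniform dosing is plausible and no effect on DLT risk can be quantified. But that 15 is the error remains an inference: it could equally be a later revision not carried into Sections 4.0 and 5.1. The Pharmacy Manual table and the website configuration might resolve the point, but neither is in the documents and neither is said to govern. Even with uniform dosing, at least one section misstates the dose of a trial arm.

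**Conclusion.** The inconsistency is real and should be corrected before level 3 is used. The documents support either 15 or 20 mcg/kg, and the choice determines what about a third of the planned patients (7 of 21) receive and what a level-3 optimal dose would mean. The conclusion rests on the text alone and needs no assumption about which value is right; the 70 kg weight serves only the volume check. It does not extend to mixed dosing within level 3, which the documents do not show, nor to the sample size or stopping boundaries. On this record the only prior patients are two at level 1, so no level-3 patient is shown as treated.

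**What to change.** The sponsor confirms the intended level-3 dose and enters that single value in Sections 4.0, 5.1 and 7.3.1. Before any patient is assigned to level 3, the sponsor checks that the Pharmacy Manual volume table and the randomisation set-up carry the same value. If a level-3 patient has been treated since this text was written, that patient's dosing record should be checked to establish which dose was given.

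The cost is a protocol wording amendment and the cross-check of those two sources. No additional patients, data or change to the statistical design is required.

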9.0 Adverse Events and Reporting Requirements

Adverse event definition:

An adverse event is the appearance or worsening of any undesirable sign, symptom, or medical condition occurring after starting the study drug even if the event is not considered to be related to study drug. Medical conditions/diseases present before starting study drug are only considered adverse events if they worsen after starting study drug. Abnormal laboratory values or test results constitute adverse events only if they induce clinical signs or symptoms, are considered clinically significant, or require therapy and otherwise meet the criteria for a reportable adverse event as defined above. They are to be captured under the signs, symptoms or diagnoses associated with them.

It is common for HCT recipients to experience multiple complications as part of the transplant itself that are unrelated to exposure to investigational agents. Symptoms of the original or targeted disease are not to be considered adverse events for this study except for hematological toxicities as defined below. From start of study treatment through 30 days from last dose of CYT107, symptoms related to the conditioning regimen will not be reported unless the event is both serious and considered by the investigator to also be possibly, probably, or definitely related to CYT107. After 30 days from the last dose of CYT107, adverse events should only be reported if they are both serious and probably or definitely related to CYT107. Events that are unlikely or unrelated to CYT107 are not required to be reported. Reporting of such events should include the investigator's assessment as to whether the event should be attributed to any of the HCT procedure itself, CYT107, GVHD, or exposure to immunosuppressive agents. An event may be attributable to all, some, or one of these categories.

Assessment of the Adverse Events Severity:

The severity of the adverse events (AEs) will be graded according to the Common Terminology Criteria v4.0 (CTCAE).

Recommended Adverse Event Recording Guidelines

Attribution	Grade 1	Grade 2	Grade 3	Grade 4	Grade 5
Unrelated	Phase I	Phase I	Phase I Phase II	Phase I Phase II Phase III	Phase I Phase II Phase III
Unlikely	Phase I	Phase I	Phase I Phase II	Phase I Phase II Phase III	Phase I Phase II Phase III
Possible	Phase I Phase II	Phase I Phase II Phase III			
Probable	Phase I Phase II Phase III				
Definitive	Phase I Phase II Phase III				

Treatment period:

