Active treatment period (ATP) is defined from the first injection of CYT107 through 30 days from

the last injection.

Time for Adverse Event (AE) Collection:

Adverse events will be collected from the first injection of CYT107 through 30 days from the last injection. AEs that occur up to 30 days from the last injection of CYT107 will be followed until resolution.

The collection of adverse events will reflect the onset and resolution date and maximum grade. If a patient is taken off study while an event is still ongoing, this will be followed until resolution or the event has stabilized. Pre-existing medical conditions will be recorded only if an exacerbation occurs during the active treatment period. Co-morbid events will not be scored separately.

Adverse Event Reporting:

The Investigator or physician designee is responsible for verifying and providing source documentation for all adverse events, and assigning attribution for each event on all subjects enrolled on this study.

Adverse events will be documented and entered into the electronic case report form (REDCap/CORe). All protocol specific data will be entered into REDCap/CORe.

Events not to be considered adverse events in this study are those related to original disease or expected in the post-allogeneic transplant period.

Isolated changes in laboratory parameters such as electrolyte, magnesium and metabolic imbalances, uric acid changes, elevations of GPT, GOT, LDH and alkaline phosphatase will not be captured.

Concomitant medications

Patients treated on this protocol will require supportive care treatment (concomitant medications). These medications are considered standard of care and have no scientific contribution to the protocol; therefore no data will be captured on various medications needed or their side effects. All concomitant medications will be captured in the medical record.

Causality Assessment.

The principal investigator will be the final arbiter in determining the causality assessment.

List of most common expected adverse events:

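### Only 19 of the 21 patients are randomised, so comparisons with dose 1 (including the optimal-dose ranking) are not fully randomised; separately, DLT attribution has no described blinding and Section 9 conflicts with the DLT list on what is recorded

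*Combined protocol and SAP*

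**What the plan says.** **Randomisation.** Section 7.3.1 gives two reasons for randomising: outcomes need not rise with dose, and "also the scientific goal to obtain unbiased comparisons between doses". It continues: "A maximum of 21 patients will be randomized among the three IL-7 doses". The allocation is fixed at seven for each dose. A later sentence changes the count. It opens "Since 2 patients previously have been enrolled and assigned to d=1" and goes on to limit the sequence to the other 19, numbered 3 to 21. Section 7.6 agrees that the sequence starts when the trial restarts at patient 3.

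**Analysis.** Section 7.5.3 selects the dose with the highest sample mean T-cell percentage of white cells at one year. The models in 7.5.2 adjust for age, graft type and disease, with no term for enrolment period. No section separates or excludes patients 1 and 2.

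**DLTs.** Part of the list in 7.1.1 is qualified by attribution to CYT107. It is unclear how far back the qualifier reaches; death comes after it. On attribution, Section 9.0 says: "The principal investigator will be the final arbiter in determining the causality assessment". Section 7.6 makes the investigator and designated personnel "responsible for recording all baseline covariates and outcome variables and implementing the within-dose stopping rule in terms of DLTs". No blinding of patient, investigator or assessor is described.

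**Recording.** Section 9.0 under Adverse Event Reporting excludes isolated GPT and GOT elevations from capture. Under AEs Data Collection it sends to REDCap only serious events and events that require dose modification. Its recording-guidelines table lists Phase I events of every grade and every attribution.

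**The concern.** Randomisation protects a comparison only among the patients it assigns. Patients 1 and 2 entered before the restart, all at one dose, and have no counterparts at doses 2 and 3. If they differ from later patients in case mix, supportive care or laboratory practice, the difference goes into the dose-1 mean and from there into the choice of optimal dose. At seven patients per dose, two patients carry real weight.

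The DLT strand is a different mechanism. Where an event counts only if judged attributable, an assessor who knows the dose may judge like events differently at different doses. The natural check is to set all listed events beside the attributed ones. That needs the unattributed events to have been recorded, and Section 9 does not make this certain.

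**Working it through.** **1. Patient count.** Inputs from 7.3.1: maximum 21, 7 per dose, 2 earlier patients at dose 1.
- 3 × 7 = 21; 21 − 2 = 19. This reproduces the plan's own 19.
- Randomised per dose: 7 − 2 = 5 at dose 1, and 7 and 7 at doses 2 and 3, if no dose closes early.
- Earlier patients: 2/7 = 28.6% of dose 1, 2/21 = 9.5% of the trial, none at doses 2 and 3.

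**2. Shift in the dose-1 mean.** Let δ be the expected difference, in SD units, between earlier and randomised patients at the same dose. The documents give no value, so a range is assumed.
- Shift = (2/7) × δ. For δ = 0.5 it is 0.14 SD; for δ = 1 it is 0.29 SD; for δ = 0 it is zero.

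**3. Effect on dose selection.** Assume normal outcomes, equal variances, complete one-year data and three equally good doses. Each dose mean then has standard deviation s = 1/√7, and dose 1 is centred at μ = 2δ/7. With φ and Φ the standard normal density and distribution functions,

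Pr(select dose 1) = ∫ (1/s) φ((x − μ)/s) Φ(x/s)² dx.

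| δ (assumed) | Shift (SD) | Pr(select dose 1) |
|---|---|---|
| 0 | 0 | 33.3% |
| +0.5 | +0.14 | 44.5% |
| −0.5 | −0.14 | 23.4% |
| +1 | +0.29 | 56.1% |
| −1 | −0.29 | 15.4% |

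**4. Randomised-only analysis.**
- Standard error of a dose-1 contrast: √(1/5 + 1/7) = 0.586 SD, against √(1/7 + 1/7) = 0.535 SD with all patients. The ratio is 1.095, about 10% larger.
- With equal doses, dose 1 is selected about 35% of the time whatever δ is. This is slightly above one third because a mean of five is more variable.
- By simulation with equal doses and δ = 0, the 5/7/7 and 7/7/7 analyses select different doses about 13% of the time and order the doses differently about 24% of the time, by chance alone.

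**5. DLT recording, provisions side by side.**
- AST and ALT elevations are DLT items in 7.1.1, yet isolated GPT (ALT) and GOT (AST) elevations are not captured under Section 9.0. Both cannot stand.
- The recording table lists unrelated and unlikely events at all grades for Phase I, and Adverse Event Reporting sends adverse events to REDCap/CORe. AEs Data Collection limits REDCap to serious events and those needing dose modification.
- Timing: three weekly doses fall on days 0, 7 and 14, so 30 days after the last dose is day 44, beyond the 42-day DLT window. For a patient who stops after the first dose it is day 30, inside the window.

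**The case against.** The best defence is that two openly disclosed earlier patients in a 21-patient early-phase study are a visible design choice, and that no bias has been shown. That stands: the concern is a risk, and it vanishes if the patients are exchangeable. Their use in the within-dose safety rule does not depend on randomisation. What the defence does not answer is that 7.3.1 calls 21 patients randomised and claims unbiased comparison for all of them.

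Three stronger readings are tempting, and the documents do not support them.

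- *Neither primary comparison is unbiased.* Cell counts and percentages involve no attribution, and doses 2 and 3 contain only sequence-assigned patients. That contrast is unaffected on cell counts.
- *Section 9 drops unrelated events from the DLT window.* The sentence "Events that are unlikely or unrelated to CYT107 are not required to be reported" follows one about the period more than 30 days after the last dose and reads as governing that period. For a patient dosed on schedule that begins after day 44. It could reach into the window only for a patient who stops early. Serious events also go to the IND Office regardless of attribution.
- *Misattribution has a known effect on the dose comparison.* If an assumed 20% of DLTs were judged unrelated, the chance that the 7.3.2 rule closes a dose with true DLT rate .55 would fall from .502 (plan: .497) to .299. But that is a within-dose stopping probability, the 20% has no source in the documents, and it discounts all DLTs although attribution governs only some. DLTs are tabulated and monitored by dose; no formal between-dose DLT comparison is planned.

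There are also safeguards. Section 7.7 sends toxicity summaries to the IND Office for review and approval, and Section 9.0 scores an event as possibly or probably related when a link cannot be ruled out. These reduce the attribution risk but do not make the assessor unaware of dose.

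**Conclusion.** The point holds in limited form. Comparisons involving dose 1, and so the raw-mean ranking in 7.5.3, are not fully randomised, contrary to the stated aim. The size of any bias is unknown. The movement from 33% to about 45% or 23% is conditional on an assumed ±0.5 SD difference, equal doses and normal outcomes; it shows how sensitive the ranking is and does not estimate what will happen.

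The DLT strand holds as a smaller point. That the investigator knows the dose is a strong inference from the absence of any described blinding and from the dose-specific stopping rule; the plan does not state it. The conflict between 7.1.1 and Section 9.0 over transaminase elevations, and within Section 9.0 over what enters the database, is plain on the text and needs no assumption.

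**What to change.** 1. **Section 7.3.1:** replace 21 randomised with 19 randomised plus 2 earlier patients assigned to dose 1, and limit the claim of unbiased comparison to the randomised patients.
2. **Section 7.5.3:** report the T-cell comparison and the optimal-dose ranking for the 19 randomised patients as a sensitivity analysis beside all 21. Do not add a rule that switches automatically when the two disagree: they select different doses about 13% of the time by chance, so disagreement alone is not a sign of bias.
3. **Sections 7.1.1 and 9.0:** reconcile them so that every event on the DLT list within 42 days of the first injection, transaminase elevations included, is recorded in the study database whatever its attribution. State which DLT items the attribution qualifier covers.
4. **Section 7.5.1:** tabulate these events by dose next to the attributed count.

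The cost is one extra analysis, one extra table, some extra recording and revised wording. The randomised-only analysis has about 10% larger standard error for dose-1 contrasts. No blinding procedure and no additional patients are needed.
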